Lavage of the Uterine Cavity for Diagnosis of Ovarian Cancer

NCT03606486

Date: 11/9/23

STUDY PROTOCOL

LAVAGE OF THE UTERINE CAVITY FOR DIAGNOSIS OF OVARIAN CARCINOMAS

PRINCIPAL INVESTIGATOR: [name]

TITLE: Associate Professor

INSTITUTION: University of Washington

ADDRESS: [name]
[name]

[contact]

Email: [contact]

CO-INVESTIGATOR: [name] [name]

Title: Assistant Professor

INSTITUTION: University of Washington

ADDRESS: [name]
[name]

Email: [contact]

Funding:

Minnesota Ovarian Cancer Alliance Early Detection Grant

SUMMARY OF PROPOSED RESEARCH

The goal of this project is to develop a minimally invasive test to detect ovarian cancer, by searching for mutations from the tumor in samples obtained from the cervix (Pap smears), and from the uterus (uterine lavage) in women with ovarian cancer and women with a genetic predisposition to malignant neoplasm of the ovary. We plan a pilot study of 60 women with ovarian cancer and with genetic predispositions to malignant neoplasm of the ovary. Pap smear and uterine lavage samples will be collected while the woman is under anesthesia for planned debulking surgery or prophylactic surgery. A novel, highly sensitive and accurate technique, Crispr-Duplex sequencing, will be used to detect tumor associated mutations in *TP53* (the most commonly mutated gene in ovarian cancer) within these samples. These results will be compared to sequencing results in the tumor itself for comparison, and Pap and uterine lavage will be compared to each other to determine the optimal test.

A. BACKGROUND AND SIGNIFICANCE

In 2017, more than 22,000 women will be diagnosed with ovarian cancer and more than 14,000 women will die from the disease, making it the leading cause of death from gynecologic cancer¹. Ovarian, peritoneal, and fallopian tube carcinoma can clinically be considered one disease, referred to collectively as OC. The majority of patients present with advanced stage III or IV disease, with 5-year survival rates of 34% and 18%, respectively². In contrast, patients diagnosed with stage I disease have 90% 5-year survival², demonstrating the critical importance of early detection. Efforts at screening for early stage OC using ultrasound and serum

biomarkers such as CA-125 have been unsuccessful at reducing mortality from this disease^{3, 4}. Women with inherited mutations in *BRCA1* and *BRCA2* are at increased risk of developing OC, with lifetime risks estimated near 50% for *BRCA1* and 20% for *BRCA2*^{5, 6}. Therefore, for high-risk women, national guidelines recommend removal of the ovaries and fallopian tubes after completion of childbearing⁷. Surgical prevention dramatically reduces the incidence of OC in *BRCA1* and *BRCA2* mutation carriers, and improves all-cause mortality^{8, 9}. Risks of surgery, premature menopause, and loss of childbearing potential are balanced against these benefits. Women at high risk need more sensitive and specific screening options when they need to delay surgery. Mathematical models have estimated that women with *BRCA1* and *BRCA2* mutations who go on to develop OC spend at least 4 years with pre-invasive or early stage (I and II) lesions¹⁰, providing a window in which an adequately sensitive screening method could lead to early detection. As these lesions are often microscopic or <1cm, they are not detected clinically by standard imaging techniques, and many early lesions will have a normal CA-125.

The limitations of CA-125 and ultrasound have led investigators to consider molecular approaches to early detection. The first demonstration that OC could be detected using minimally invasive sample collection came from Kinde et al, sequencing DNA from Pap smears¹¹. Using an error-corrected next generation sequencing (NGS) method called Safe-SeqS, they were able to detect mutations in tumor DNA in 41% of Pap smears from women with OC. To improve the yield of tumor DNA, Speiser and Zeillinger developed a uterine lavage technique that allows for collection of samples from closer proximity to the OC. As the ovaries, fallopian tubes, and uterine cavity are in communication with each other, they hypothesized that uterine lavage could reliably capture OC DNA. They sequenced DNA from uterine lavage samples using NGS for a panel of potentially mutant genes, and were able to identify OC related mutations in 18/30 (60%) cases, with most being in the gene *TP53*¹². Additional tumor mutations were identified in an additional 6 uterine lavage samples that were tested with digital droplet PCR (ddPCR), once the tumor specific mutation was determined by sequencing the OC itself. While this demonstrates an important proof of principle that the mutation can be detected, it is not helpful as a screening test as it would require a biopsy of the OC first. Given these studies' limitations in sensitivity, other sequencing techniques are needed in order to make this type of testing feasible.

Next generation sequencing techniques commonly introduce low-level errors that can appear to be mutations, masking true tumor-associated mutations that are present at very low frequencies, as would be expected for early stage cancers. In order to not miss these true mutations, substantial improvements to these methods are needed. Duplex Sequencing (DS), developed in the Loeb lab at the University of Washington¹³, overcomes this problem by reducing the error rate to <1 in 10 million. This accuracy is accomplished by independently sequencing the two strands of each DNA molecule, as true mutations will be present at the same position in both strands, and artifacts or errors are present in only one of the two strands. [name] and colleagues have utilized DS to accurately detect mutations as infrequent as 4×10^{-4} in tumor DNA taken from peritoneal fluid samples in women with OC¹⁴. They then began collaborating with the investigators that developed the uterine lavage technique described above, and sequenced *TP53* in uterine lavage samples from OC patients with DS, identifying mutations in 8/10 (80%) samples (see preliminary data). *TP53* is mutated in >96% of high-grade serous OCs¹⁵, in addition to most serous tubal intraepithelial carcinomas (STICs)¹⁶, making *TP53* an optimal target for OC early detection. The main difficulty with DS is that efficiency is

low (~1%), requiring at least 1 μ g of DNA to achieve adequate sequencing coverage. Utilizing Crispr- Cas9 genome fragmentation, rather than random sonication, increases efficiency and requires much less input DNA.

Preliminary data:

In collaboration between the University of Washington and the Medical University of Vienna, DS was applied to 10 uterine lavage samples from women with OC, and 11 controls. Tumor associated *TP53* mutations were detected with DS in 8/10 (80%) women with OC, and not in controls, manuscript in preparation by [name] et al. Interestingly, biological background mutations in *TP53* were found in all tested subjects, including the healthy controls, a finding that was also present in the previous study of DS using peritoneal fluid from women with and without OC¹⁴. Tumor related *TP53* mutations tended to have higher allele frequencies, and in this study a cutoff of 0.01 was effective at differentiating between these two findings. Moreover, this threshold allowed for discrimination between women with OC from controls with 70% sensitivity and 100% specificity, a diagnostic performance superior to any other OC test currently available. Preliminary data suggests that filtration of the uterine lavage samples to remove clusters of endometrial cells results in an increased allele frequency of tumor associated mutations, and ongoing efforts are optimizing this protocol. This study provides evidence that uterine lavage combined with DS increases the sensitivity of tumor *TP53* mutation detection over other sequencing methods.

B. General Description of the Study

This study aims to collect specimens from 50 women with high-grade serous OC and 10 women who are undergoing prophylactic surgery for genetic predisposition to malignant neoplasm of the ovary, while they are under anesthesia for planned surgery at a single site, the University of Washington. There will be a total of at least 60 participants in the study.

[name] will coordinate the collection of samples including a Pap smear, uterine lavage, and tumor at the time of planned primary surgery. DNA will be extracted from all samples. [name] will coordinate the *TP53* sequencing utilizing the Crispr-DS method on the Pap smear and uterine lavage extracted DNA. Primary tumors will be sequenced in order to confirm that the mutations identified in the Pap and/or uterine lavage are present in the tumor. We will compare the sensitivity for OC detection of Pap smear compared to uterine lavage, in order to optimize our assay.

Results will not be released to either patients or clinicians, or used for any treatment decisions.

C. Study Objectives

Objectives:

- 1) To collect samples from 50 women with high-grade serous OC and 10 women who are undergoing prophylactic surgery for genetic predisposition to malignant neoplasm of the ovary, including Pap smears, uterine lavage, and a tumor sample.
- 2) To test the DNA from Pap smears and uterine lavage samples for tumor-derived *TP53* mutations, using the new technology of Crispr-Duplex Sequencing.
- 3) Determine the sensitivity and specificity of Pap smear or uterine lavage in detection of tumor-derived *TP53* mutations.

D. Study Design

Study population and recruitment:

Patients with suspected OC and women who are undergoing prophylactic surgery for genetic predisposition to malignant neoplasm of the ovary will be identified and consented pre-operatively for participation in the study. This process is already in place at the University of Washington as nearly all patients with OC or those undergoing prophylactic surgery for genetic predisposition to malignant neoplasm of the ovary are consented pre-operatively for our Gynecologic Oncology Tissue Bank.

Eligibility:

Inclusion criteria:

- Women over the age of 18 with suspected ovarian cancer or genetic predisposition to malignant neoplasm of the ovary
- Planned surgery
- Have a uterus and no history of tubal occlusion

Exclusion criteria:

- Unable to speak English
- Unable to provide informed consent
- Prior hysterectomy

Sample collection:

After induction of anesthesia, samples will be collected, starting with a standard liquid-based Pap smear. Uterine lavage is then carried out. First the cervix is cleansed with a betadine solution as is standard prior to surgery involving the uterus. The three-way endometrial catheter is then inserted into the cervical canal and 10ml of sterile saline are used to irrigate the uterine cavity, as previously described¹². The three-way uterine lavage catheter developed by Oncolab Diagnostics has received FDA designation as a nonsignificant risk (NSR) device. It is commercially available, and is currently being utilized in 3 ongoing clinical trials (NCT02039388, NCT02062697, and NCT02518256). Finally, samples of the OC itself are collected for those with suspected OC during the abdominal surgery for comparison. Uterine lavage samples will be filtered to remove clusters of endometrial cells to decrease the amount of non-tumor DNA.

Molecular analysis:

DNA will be extracted from each of the three samples collected per case (Pap, uterine lavage, and tumor). Pap smear and uterine lavage samples will be sequenced for *TP53* mutations using the Crispr-Duplex Sequencing method. Patients will be excluded from the study if the diagnosis of high-grade serous OC is not confirmed by the final pathology results.

Data collection:

Baseline demographic and clinical variables will be collected on each patient per procedures already in place with our gynecologic oncology Tissue Bank.

Data privacy and Safety Monitoring:

There will be limited access to authorized users who will use password protection and encrypted storage devices. Data will be stored in a locked cabinet on an encrypted flash drive. Access to electronic records are password protected. Team members will complete confidentiality and security training. No identifiers will be used in any study reports, publications or presentations.

Adverse Events:

Adverse events are unlikely with this study. Enrolled subjects are women who are already planned to undergo surgery for their suspected ovarian cancer, and they will be under anesthesia during collection. Collection is designed to occur in parallel with other portions of the surgery, so we do not anticipate it will prolong surgical time. Uterine perforation or bleeding, or a pelvic infection could occur, although it is unlikely based on the known safety of procedures such as endometrial biopsy. If any such adverse events occur, they will be reported.

References:

## **Lavage of the Uterine Cavity for Diagnosis of Ovarian Carcinomas Statistical Analysis Plan**

Comparison of mutation frequencies, mutation burden, and variant allele fraction (VAF) across groups of individuals was performed by Mann-Whitney U test. Correlations were tested with Spearman's rank test. Associations between categorical variables were tested with Fisher exact test. Two logistic regression models were constructed, one including the standard ovarian cancer risk variables (age and CA-125) and an exploratory model including age, CA-125 and TP53 mutation burden. The models equated the relationship between variables with the occurrence of ovarian cancer to estimate beta coefficients with 95% confidence intervals. Due to a heavy right-tailed distribution, CA-125 was log transformed. Age and TP53 mutation burden were presented as a per standard deviation (SD) increase. All tests were two-sided at an alpha level (type 1 error rate) of 0.05. Statistical analyses were performed with SPSS version 26, R version 4.1.1, and Stata 16.

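### The visible SAP text gives no sensitivity, specificity or within-woman Pap-versus-lavage analysis, and tumor-confirmed detection cannot yield an informative specificity in the prophylactic women

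*SAP*

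**What the plan says.** **What is promised.** Objective 3 (Protocol, C. Study Objectives) reads "Determine the sensitivity and specificity of Pap smear or uterine lavage in detection of tumor-derived" TP53 mutations. Section B of the protocol adds "We will compare the sensitivity for OC detection of Pap smear compared to uterine lavage, in order to optimize our assay". The Summary of Proposed Research says "Pap and uterine lavage will be compared to each other to determine the optimal test". Both specimens come from each woman at the same operation.

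**What counts as detection.** Section B states "Primary tumors will be sequenced in order to confirm that the mutations identified in the Pap and/or uterine lavage are present in the tumor". No allele-frequency threshold or other call rule is set for this study's specimens. Preliminary data reports a 0.01 allele-frequency cutoff, but only as a result of the earlier lavage study.

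**Who supplies tumor.** Objective 1 covers both groups and describes the samples as "including Pap smears, uterine lavage, and a tumor sample". Sample collection (D. Study Design) takes tumor only from women with suspected OC.

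**Who stays in.** Molecular analysis (D. Study Design) says "Patients will be excluded from the study if the diagnosis of high-grade serous OC is not confirmed by the final pathology results".

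**What is analysed.** In the SAP text, comparison of mutation frequencies, burden and allele fraction "across groups of individuals was performed by Mann-Whitney U test". Spearman and Fisher tests follow, then two logistic models for cancer occurrence: "The models equated the relationship between variables with the occurrence of ovarian cancer to estimate beta coefficients with 95% confidence intervals". The SAP body never mentions sensitivity, specificity, Pap smear, a positivity rule or a paired method. It does not say which specimen supplies the TP53 mutation burden.

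**The concern.** Objective 3 is the protocol's only estimation objective, and the listed analyses do not produce its result. A logistic coefficient describes how mutation burden relates to having cancer. It does not say in what fraction of cases a specimen detects the tumor's mutation.

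The definition matters as much as the missing method. If a positive result must be confirmed in the woman's tumor, women without a tumor cannot test falsely positive, and specificity is 100% whatever the assay finds. If any TP53 mutation counts, specificity would be expected near zero. A rule between these extremes is needed, and none is adopted. Left open, it could be chosen after the results are seen. The reported specificity and the choice between Pap and lavage would then both depend on it.

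**Working it through.** **1. Match each promise to a listed method.**

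| Promised result | Mann-Whitney | Spearman | Fisher | Logistic models |
|---|---|---|---|---|
| Sensitivity, per specimen | no | no | no | no |
| Specificity, per specimen | no | no | no; tests association only | no; no ROC curve or cut-point listed |
| Pap versus lavage, same woman | no; assumes independent groups | no; shows correlation, not which detects more | no; assumes independent samples | no |

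**2. Specificity under each available definition.** Specificity = negatives / (negatives + false positives) in women without cancer. The prophylactic group (n = 10) is the only planned group without cancer. That it is meant to supply specificity is an inference, since no section says so.

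- Tumor-confirmed rule: with no tumor sample, confirmed positives are 0 by construction. Specificity is 10/10 = 100%, or undefined, and carries no information about the assay.
- Any-mutation rule: Preliminary data found background TP53 mutations in every subject, controls included. Expected specificity is near 0%.
- Tumor-independent cutoff: estimable. The pilot's 0.01 cutoff shows this can work, but it is not adopted here.

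**3. The rule moves the answer in the pilot.** Preliminary data gives 8/10 = 80% by tumor-associated detection, and 70% sensitivity with 100% specificity at the cutoff, in 10 cases and 11 controls. The counts at the cutoff are not stated; 7/10 and 11/11 are implied. Clopper-Pearson 95% limits are the 0.025 quantile of Beta(x, n−x+1) and the 0.975 quantile of Beta(x+1, n−x):

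- 8/10: 44% to 97%
- 7/10: 35% to 93%
- 11/11: 72% to 100%

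The two rules differ by one woman in ten, 10 points.

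**4. Precision at the planned sizes (50 cases, 10 prophylactic women).** Counts are illustrative.

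| Quantity | Count | 95% CI |
|---|---|---|
| Sensitivity | 30/50 | 45% to 74% |
| Sensitivity | 35/50 | 55% to 82% |
| Sensitivity | 40/50 | 66% to 90% |
| Specificity | 10/10 | 69% to 100% |
| Specificity | 9/10 | 55% to 99.7% |

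When all n are negative the lower limit is 0.025^(1/n). For n = 10 this is 0.692.

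**5. Why the paired table is needed.** The documents do not give the Pap/lavage overlap, so this is an assumed example: lavage 30/50, Pap 20/50, difference 20 points. Let b = lavage only and c = Pap only. Fisher's test gives p = 0.071 whatever the overlap. The paired result depends on it:

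| Positive on both | b, c | Tango 95% CI for the difference | Score McNemar (b−c)²/(b+c) | p |
|---|---|---|---|---|
| 0 | 30, 20 | −8 to 45 points | 100/50 = 2.00 | 0.157 |
| 12 | 18, 8 | 0.01 to 38 points | 100/26 = 3.85 | 0.0499 |
| 20 | 10, 0 | 11 to 33 points | 100/10 = 10.0 | 0.002 |

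The example shows that pairing carries information. It does not measure an error in the plan.

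**6. Test and interval should match.** In the 18 versus 8 row the exact McNemar p is 0.076, while the Tango interval just excludes zero (0.0001 to 0.384). The score test agrees with the interval. Naming an exact test beside a score interval would leave it unclear which governs.

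**The case against.** **It is a pilot, and proportions need no listed test.** This stands in part. The protocol promises a comparison to optimize an assay, not a hypothesis test, so no p-value is required. But a proportion still needs a definition of positive, a denominator, and a rule for women with one evaluable specimen. None is stated.

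**The protocol already shows a workable rule.** True of the pilot's 0.01 cutoff. So a reader should not infer that specificity cannot be defined; the gap is that no definition is adopted. The cutoff also comes from lavage samples under Duplex Sequencing. Nothing in the documents shows that it carries over to Pap smears or to the Crispr-based method.

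**The exclusion deletes the prophylactic group.** A reader might infer from the Molecular analysis sentence that the specificity denominator falls from 10 to 0. The context does not support that. The paragraph concerns cases with three samples, and other sections plan for 10 prophylactic women. The likely intent is to drop women with suspected OC whose pathology is not high-grade serous. The sentence needs a clarifying clause and is not evidence of a lost group.

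**The SAP as a whole may cover this.** Part of the SAP file was not seen. It may be only front matter, but that cannot be confirmed, so omission from the whole SAP cannot be claimed.

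**The analysis seems already done.** The SAP is written in the past tense. That limits the remedy to a labelled addition if results are known; it does not remove the gap.

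**Conclusion.** The point holds for the visible SAP text and the protocol. No listed analysis yields sensitivity, specificity or a within-woman Pap-versus-lavage result. The tumor-confirmed concept, under the collection procedure described, makes specificity in the prophylactic women 100% by construction or undefined. In the pilot the choice of rule moved sensitivity by 10 points (one woman in ten). A perfect 10/10 would still be compatible with a specificity as low as 69%.

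This rests on three assumptions: that the prophylactic women are the intended non-cancer group, that tumor is collected only for suspected OC despite the wording of Objective 1, and that the unseen SAP text does not supply the analysis. The documents do not support a verdict that the plan is fatally flawed or that the non-cancer group is lost. Severity: should fix. Confidence: moderate, pending the unseen text.

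**What to change.** Add a dated Objective 3 analysis to the SAP, labelled post hoc if results are already known.

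1. **Positivity rule.** State a tumor-blind rule for each specimen type, applied alike in cases and prophylactic women. The 0.01 cutoff is one candidate; show results at other cutoffs. Report tumor-matched detection separately, in cases only.
2. **Accuracy estimates.** For each specimen, report sensitivity in confirmed cases and specificity in prophylactic women, with Clopper-Pearson 95% CIs. Treat specificity as descriptive only.
3. **Paired comparison.** In cases, show the 2×2 Pap/lavage table and make the paired difference in sensitivity with a 95% CI (for example Tango score) the primary result. If a p-value is wanted, use the matching score McNemar test. State how women with one evaluable specimen are counted.
4. **Reconcile the protocol.** Clarify that the pathology exclusion applies to women enrolled for suspected OC and not to the prophylactic group. Reconcile the tumor-sample wording of Objective 1 with Sample collection.

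The listed methods can stay for comparisons between different women.

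**Cost.** A few sentences and a small amount of analysis on specimens already planned. Whether all paired results exist is not documented. Intervals will be wide, specificity will look less favorable than a bare 100%, and prespecification cannot be restored if results are known.
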